4.2. Anticipated adverse device effects

Mantis Photonics performed a risk analysis concerning the anticipated adverse investigation device effects. Some small anticipated adverse events resulting from insufficient or inadequate instructions for use, deployment, installation, operation or any malfunction of the investigational medical device are identified and described in the risk analysis report of Mantis Photonics. The severity and occurrence ranking of those identified and described adverse events are no unacceptable risks of harm to the subject, the administering investigator, nor third party involved in this investigational device when used under normal conditions and for its intended use.

4.3. Risks associated with participation in the clinical investigation

Mydriatic retinal scans are common procedures in ophthalmological practice. It can be considered a low-risk intervention due to its non-invasive nature. Subjects can experience some inconvenience by the flash light (e.g., pain and discomfort, redness, itching and/or blurriness), but this is not dangerous. Mantis Photonics consciously makes use of a commercial retinal camera set-up in which only the camera is replaced. This means that the subjects experiences, including the flash lamp are identical to the experience of tested and verified retinal scan devices.

A known risk of the mydriatic retinal scan procedure is the effect of the pupil dilating eye-drops. The glare effect causes the patient to be unfit to drive a vehicle for a period of about 4 hours. The effect ends after about 4 hours without lasting consequences.

Based on a risk assessment that Mantis Photonics performed, it can be concluded that for the investigational device (incl. the administration of the fluid eye drops of tropicamide 1% and phenylephrine hydrochloride 10%), there are no unacceptable risks of harm to the subject, the administering investigator, nor third party involved in this investigational device when used under normal conditions and for its intended use.

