
Study objectives:
	
Primary objective: To evaluate the performance of the hyperspectral camera for non-invasive retinal examination in order to improve the diagnosis of diseases affecting the retina or central nervous system.
 
Secondary objective: To investigate the possibilities of the use of a hyperspectral camera for non-invasive retinal examination.
 
Safety objective(s): To evaluate the safety of the hyperspectral camera for non-invasive retinal examination by assessment of device deficiencies and adverse events, non-serious and serious, rated for causality.

Study endpoints:
	
Primary endpoints: To evaluate the effectiveness of the hyperspectral imaging of retinal changes by detecting structures and conditions in the retina and to compare the hyperspectral imaging with other diagnostic techniques. More specifically, can the hyperspectral camera detect the different structures of the retina based on spectral distribution? Can the hyperspectral camera detect differences in oxygenation levels between arteries and veins in healthy retina and retina with disease?
 
Secondary endpoint: To investigate if additional signs of reduced oxygenation can be seen in retinal disease. More specifically, can optic nerve thinning be detected by hyperspectral camera? Can hyperspectral imaging detect changes that are not measurable with other examination modalities and do these differ from normal retinal changes?
 
Safety endpoint(s):
 
 1. Incidence of AE/ADE/SAE/SADE/DD. 2. Incidence of AE/ADE/SAEE/SADE/DD leading to withdrawal of a subject. 
The experience of having a temporary, benign after-image of the flash lamp for a brief period is common. The mydriatic eye drops can be temporary unpleasant (pain and discomfort, redness, itching and/or blurriness). Those effects are expected and explained during the informed consent phase before including the subject in the trial. Those effects should not be qualified as unacceptable risks of harm to the subject, and therefore those effects are no reason to stop the clinical investigation, unless the subject wants to withdrawal from the clinical investigation.

Planned duration of the clinical investigation:
	
Estimated date of first subject enrolled: Q3 2022.

Estimated date of last subject completed: Q2 2023.

Estimated date of end of clinical investigation (database lock) is Q4 2023.

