2.3. Target population

A healthy population and a patient-population with an ophthalmological disease affecting the retina.

2.4. Detailed description of the investigational device and materials coming into contact with the human body

None of the components of the investigational device will be in contact with tissues or body fluids of the subjects.

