4.5. Steps to be taken to control or mitigate risks

The medical, nursing and other staff members of the investigation site will be trained on how to use the investigational device (incl. the administration of the fluid eye drops of tropicamide 1% and phenylephrine hydrochloride 10%) and subjects will be closely monitored during the clinical investigation.

AE's, ADE's, SAE's and DD's will be registered throughout the clinical investigation.

5. Objectives and hypotheses of the clinical investigation

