6.4. Description of the clinical procedures and methods relating to the clinical investigation

Recruitment of healthy subjects is done through local advertising. Recruitment of patient-subjects with eye disease is done at the clinic Sundets Öganläkare.

Coordinated registration and allocation of participant trial numbers will be required to enroll all participants (see section 6.3). The Principal Investigator ensures through the Informed Consent Form that the trial objective, process and all trial subject rights are clear to the subject.

All participants (healthy subjects and patient-subjects) are considered to be enrolled into the clinical trial following the informed consent is signed, the evaluation of the medical history and the inclusion criteria, confirmation of eligibility, completion of the registration, allocation of the participant trial number and the investigation performance phase.

The overall purpose is to investigate if the investigational device can produce clear hyperspectral imaging of retinal changes by detecting structures and conditions in the retina and to compare the hyperspectral imaging with the expert diagnosis, as well as to investigate if additional signs of reduced oxygenation can be seen in retinal disease.

The admission visit (visit 1) is carried out as planned with visual acuity, refraction, pressure, field of view (if applicable), OCT and corneal microscope examination. Records of age and sex, other diseases and treatment are obtained. The subject will be administered pupil dilating drops of tropicamide 1% and phenylephrine hydrochloride 10% are instilled in each eye at the time of the examination. Images of the retina of the subject will be taken with the use of the Mantis Photonics hyperspectral camera by the medical staff members at the investigational site. The subjects are usually sent home after the image is taken when there are no inconveniences for the subjects.

The overview of the clinical investigation provides a review of each visit describing clinical investigation-related procedure(s) the subject undergoes during each visit:

Procedure	Visit 1 - part 1	Visit 1 - part 2	Visit 1 - part 3
	Admission & screening phase	Application of the investigation device phase	End phase
Informed consent	x		
Inclusion/exclusion criteria	x		
Medical history review	x		
Eligibility	x		
Administration of eye drops and flashlight taking image		x	
Adverse Events review		x	x
Clinical investigation end			x

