13.1.4 Serious Adverse Device Effect

A Serious Adverse Device Effect (SADE) is an ADE that has resulted in any of the consequences characteristic of a serious adverse event.

SAE's related to procedures imposed by the Clinical Investigation Plan but not with the use of the device shall not be considered Serious Adverse Device Effects.

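### The plan does not place mydriatic-drop effects consistently on the device or the procedure side, so ADE incidence depends on which section is followed

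*Combined protocol and SAP*

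**What the plan says.** **Where the drops sit.** Section 4.5 has staff "trained on how to use the investigational device (incl. the administration of the fluid eye drops", and 4.3 uses the same parenthesis when it gives the risk conclusion for the device. Elsewhere the device is hardware only. The synopsis identifies it as a hardware device, the component table in 2.1 lists no drops, and 2.4 states: "None of the components of the investigational device will be in contact with tissues or body fluids of the subjects". Section 6.4 says that the drops "are instilled in each eye at the time of the examination". Section 4.3 also describes the drop effect as a known risk of the mydriatic scan procedure.

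**What causes the symptoms.** Section 4.3, on the flash: "Subjects can experience some inconvenience by the flash light (e.g., pain and discomfort, redness, itching and/or blurriness". The synopsis, under the safety endpoints: "The mydriatic eye drops can be temporary unpleasant (pain and discomfort, redness, itching and/or blurriness". In the synopsis the only effect linked to the flash is a brief after-image.

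**What is counted.** The synopsis and 5.2 make ADE incidence, and ADE leading to withdrawal, safety endpoints. Section 13.1.2 defines an ADE as an AE related to use of the device. Section 13.2.3 asks for the relationship of each AE to the device and to the procedure, then classifies each event on one four-level scale. Section 7.4 says that all endpoints will be summarised, but specifies only frequency counts of subjects with AEs.

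**The concern.** The line between device and procedure decides whether an AE is also an ADE, and the plan puts drop effects on both sides of it. These effects are likely to make up much of the safety data: every subject is to receive drops in each eye, and 2.5 has pain, redness, itching, blurriness and pupil dilation recorded before and after the scan for all subjects. Section 13.1.1 counts anticipated events as AEs. The synopsis says that these effects are expected and are not unacceptable risks, but does not exempt them from the counts.

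At stake is the interpretation of a stated safety endpoint in a pilot of a prototype camera. Two people could tabulate the same records by different sections of the plan and report different ADE incidences, and the reader could not tell how much of either belongs to the camera.

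**Working it through.** The plan states no ADE or symptom rate, and 7.1 rules out hypothesis testing, so there is no figure to reproduce beyond the sample size: about 100 patients + 20 healthy subjects = 120.

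**Step 1: the boundary, section by section.**

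| Place | What it implies for drop effects |
|---|---|
| 4.3, risk conclusion | Device, or its use |
| 4.5, training | Device, or its use |
| 4.3, known risk | Procedure |
| Synopsis and 2.1, device description | Not part of the hardware |
| 2.4, no contact | Not a component, by inference; the drops are not named |
| 6.4, schedule table | Drops and flash share one row, under application of the device |
| 13.2.3, causality | Not assigned to either side |

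**Step 2: whether the causality rating settles it.** Levels 2 and 3 name the device and the procedures as alternatives, level 4 covers either, and all three are titled by relation to the investigation. Events whose relatedness cannot be assessed go to level 2. A rating at levels 2 to 4 therefore does not by itself show whether the event is an ADE. The explicit duty to distinguish device from procedure is written for SAEs, while the expected symptoms are ordinarily non-serious.

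**Step 3: effect on the endpoint.** Let f be the number of subjects with at least one camera- or flash-related AE, and d the number whose only related AEs are attributed to the drops.

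- Drops counted as device use: ADE incidence = (f + d)/120.
- Drops counted as procedure: ADE incidence = f/120.
- Difference = d/120, whatever f is.

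On the first reading, the split between flash and drops does not change the total. On the second it does, and this is where the conflicting symptom attributions matter.

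**Step 4: illustration.** The share d/120 is an assumption; the documents give none. Set f = 0. Intervals are exact (Clopper-Pearson) 95%.

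| Assumed share with drop symptoms only | Drops as device use | Drops as procedure |
|---|---|---|
| 5% | 6/120 = 5% (1.9 to 10.6) | 0/120 (0 to 3.0) |
| 10% | 12/120 = 10% (5.3 to 16.8) | 0/120 (0 to 3.0) |
| 25% | 30/120 = 25% (17.5 to 33.7) | 0/120 (0 to 3.0) |
| 50% | 60/120 = 50% (40.7 to 59.3) | 0/120 (0 to 3.0) |

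The upper limit for zero events is 1 − 0.025^(1/120) = 3.0%.

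**Step 5: what does not move.** AE incidence is the same on both readings. Under 13.2.2 the sponsor reports SAEs related to the device or to the investigation procedure, so reporting to the authority does not turn on this boundary.

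**The case against.** The best defence is that one reading reconciles most of the text. The drops are not a component, which satisfies 2.1 and 2.4, but giving them is part of using the device, which is how 4.5 and the schedule in 6.4 can be read. An ADE is defined by use, so flash and drop symptoms would both be ADEs. Section 13.1.5 expects associated procedures to be in the risk assessment, which would explain the parenthesis in 4.3. This reading is available, but the plan never adopts it, and 4.3 itself calls the drop effect a procedure risk.

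Other parts of the defence stand and limit the point:

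- Section 2.4 does not mention the drops. Their exclusion is an inference.
- The symptom attributions are not exclusive. The list in 4.3 is given as examples, the synopsis says only what the drops can do, and two causes can produce the same symptom.
- Section 13.2.3 already asks for both relationships for each AE. The CRF and the risk analysis report are not among the documents and may separate them.

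A reader might infer from 13.1.4 that procedure events in general are not device effects, since procedure-related events "but not with the use of the device shall not be considered Serious Adverse Device Effects". That sentence concerns SAEs, and 13.1.2 has no matching exclusion for non-serious events. It does not settle how redness or blurriness is counted.

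**Conclusion.** The inconsistency is real and affects ADE incidence and ADE leading to withdrawal. It is more than missing detail, because the existing sections point in different directions on a stated endpoint and the four-level scale does not resolve them.

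Its size cannot be stated. The gap equals the share of subjects whose only related events are attributed to the drops, and the documents give no rate. The contrast of 12/120 with 0/120 rests on an assumed 10%, and the zero also needs the flash to cause no such symptoms, although 4.3 says that it can.

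A reader might conclude that ADE incidence is undefined. The documents do not support that: the ADE is defined, and both relationships are to be assessed. What is missing is a consistent rule for the drops. Nothing here suggests that total AE counts or SAE reporting to the authority are compromised.

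**What to change.** 1. Reconcile the synopsis, 2.4, 4.3 and 4.5 to one statement of whether drop effects count as device or procedure effects, refer to it from 13.2.3, and align the symptom wording in the synopsis and 4.3.
2. In the CRF, rate causality separately for camera/flash and for drops/procedure, allowing both or unknown.
3. In 7.4, report ADE incidence with and without drop-attributed events. Say in advance that only events attributed to the drops alone are removed for the second figure, so that events rated both or unknown stay in each count.

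This should be in place before the first subject is imaged, because a single pooled rating cannot be split reliably afterwards. The cost is some rewording, one CRF field if it is not already there, and one extra table line. Some attributions will remain uncertain, since drops and flash are given at the same visit and 6.1 defines no control group; the both and unknown categories make that visible. No change to the drops or to the visit is implied.

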4.4. Possible interactions with concomitant medical treatments

There are no possible interactions with concomitant medical treatments identified in the risk analysis report performed by Mantis Photonics AB.

4.5. Steps to be taken to control or mitigate risks

The medical, nursing and other staff members of the investigation site will be trained on how to use the investigational device (incl. the administration of the fluid eye drops of tropicamide 1% and phenylephrine hydrochloride 10%) and subjects will be closely monitored during the clinical investigation.

AE's, ADE's, SAE's and DD's will be registered throughout the clinical investigation.

5. Objectives and hypotheses of the clinical investigation

5.1. The purpose of the clinical investigation

The clinical investigation is undertaken to investigate the performance of the hyperspectral camera for retinal non-invasive examination through the observation of retinal oxygenation.

5.2. Objectives

The primary objective and outcome variable are shown in the table below:

Primary objective	Primary outcome variable
To evaluate the performance of the hyperspectral camera for non-invasive retinal examination in order to improve the diagnosis of diseases affecting the retina or central nervous system.	Effectiveness of the hyperspectral imaging of retinal changes and retinal structures in terms of detecting: 
 - Different structures of the retina based on spectral distribution. - Ability to measure the blood oxygenation with an acceptable repeatability - Demonstrate differences in blood oxygenation levels for healthy retinas; above 95% in arteries and below 70% in veins.

The secondary objective and outcome variable are shown in the table below:

Secondary objective	Secondary outcome variable
To investigate if additional signs of reduced oxygenation can be seen in retinal disease. More specifically, can optic nerve thinning be detected by hyperspectral camera? Can hyperspectral imaging detect changes that are not measurable with other examination modalities and do these differ from normal retinal changes?	Effectiveness of the hyperspectral imaging in terms of detecting: 
 - Signs of reduced oxygenation be seen in retinal disease Ischemia detection in the retina. - Optic nerve thinning. - Changes that are not measurable with other examination modalities.

The safety objective and outcome variables are shown in the table below:

Safety objective	Safety outcome variable
To evaluate the safety of the hyperspectral camera for non-invasive retinal examination by assessment of device deficiencies and adverse events, non-serious and serious, rated for causality.	
- Incidence of AE/ADE/SAE/SADE/DD.- Incidence of AE/ADE/SAEE/SADE/DD leading to withdrawal of a subject.

6. Design of the clinical investigation

6.1. General information

This single centre, open, controlled investigation will be conducted at the clinic of Sundets Ögonläkare, Helsingborg (patients and healthy subjects).

In this study, patients with known retinal oxygenation problems and volunteers without known or suspected retinal pathologies will be subjected to retinal scanning. The trial's aim is not to demonstrate any treatment effect between the treatment group and the control group. Thus, no control group is defined. The study objective is the demonstration of the feasibility and applicability of the technique.

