3.1. Background

1. BENEFITS OF DETECTION OF LOW OXYGENATION REGIONS IN THE RETINA

The Western population is getting older. This is of course a positive development, but more and more people are also suffering from age-related diseases such as glaucoma and yellow spot changes that reduce vision and quality of life (Flaxman, et al. 2017). Diabetes is another disease whose complications affecting the retina are increasing in prevalence (Zimmet, et al. 2016).

The diagnosis of retinal diseases has improved in recent years with the advent of refined imaging techniques such as OCT and Ultrasound and functional tests such as automated perimetry. However, there is still a need to improve our understanding of the pathogenesis of several eye-related diseases. In the development of diabetic retinopathy, a disturbed oxygenation of the tissues with elements of hypoxia plays a role (Hardarson en Stefánsson 2012). In the development of glaucoma, there is also a discussion of an element of ischemia as an etiology (Lee, et al. 2021). To measure the degree of perfusion in the retina, angiography can be performed. However, this is time-consuming and invasive, also associated with certain risks for patients. Therefore, there is a need to improve and simplify the diagnosis and to measure the oxygenation of retinal tissues in a more convenient way.

Through shared ontogeny, the retina shares similar functions to the brain and spinal cord in terms of anatomy, functionality and immunology (De Groef en Cordeiro 2018) (London, Benhar en Schwartz 2013). There are several ocular markers for stroke and MS (London, Benhar en Schwartz 2013). There are also several similarities between disease markers for Alzheimer's disease, age-related macular disease and glaucoma (Sivak 2013). In Alzheimer's disease, which primarily affects the brain, increased beta amyloid deposition is also seen in the retina and in patients with glaucoma and age-related macular disease, increased deposition of beta amyloid and tau protein, for example, is seen in the tissues (Sivak 2013). Good retinal imaging and functional testing is therefore important to detect diseases affecting the retina but also as a means of detecting diseases that do not primarily affect visual function. The retina is therefore opening up as a structure suitable for non-invasive detection not only of retinal diseases but also an opportunity for early diagnosis and monitoring of, for example, Alzheimer's disease.

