6.3. Subjects

Inclusion criteria

For inclusion in the clinical investigation, the subject must fulfill all of the below criteria prior to enrollment and after enrollment (i.e., screening phase and enrollment phase).

For inclusion in the investigation of patient-subjects:

1. Age > 18 years.
2. Ophthalmological disease, disorder, illness or problem.
3. Provision of informed consent i.e., subject must be able to understand and sign the patient information and consent form.

For inclusion in the investigation, the healthy subjects:

1. Age > 18 years.
2. Without known eye disease.
3. Provision of informed consent i.e., subject must be able to understand and sign the patient information and consent form.

Exclusion criteria

Subjects who meet any of the below criteria, during screening phase and/or enrollment phase) will be excluded from the investigation.

For the exclusion of patients-subjects:

1. Patients with narrow-angle glaucoma.
2. Inclusion in other ongoing investigations at present that would preclude the subject from participating in this investigation as judged by the Principal Investigator.

For the exclusion of healthy subjects:

1. Presence of eye disease, eye trauma, diabetes or pregnancy.
2. Inclusion in other ongoing investigations at present that would preclude the subject from participating in this investigation as judged by the Principal Investigator.

Subject eligibility

Once written informed consent has been obtained, the Case Report Form and Subject prescreening and screening log will be completed to document adherence to the inclusion and exclusion criteria.

Where a subject fails to fulfil any element of the inclusion and exclusion criteria, this will be documented and the signed consent form and completed inclusion/exclusion criteria retained by the Principal Investigator. The subject will not be advanced any further into this clinical investigation.

Subject identification

When a subject is identified and considered eligible for entry to this clinical investigation, the subject will be allocated the next available investigation number (i.e. enrolment number) and the enrolment of the patient must be recorded in the Subject Enrolment Identification log.

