After the phases above, the retinal images are taken and analyzed. Researchers such as (Meinke 2007) have demonstrated how one can estimate the blood oxygenation at a given location (image pixel) based on the frequency absorbance spectrum. The reference frequency absorbance spectrum of fully oxygenated blood (100% oxygenation) and fully oxygen-depleted blood (0% oxygenation) are known and tabulated by comparing the pixel's frequency spectrum to the frequency absorbance spectrum of two reference curves allows us to estimate the oxygenation of the blood at the respective location.

We will compare oxygenation between arteries and veins. The largest artery and vein at the superior and the inferior temporal vascular tree will be marked for each eye. We will analyze 10 to 20 consecutive points from the papillary edge along the vascular tree to measure the mean vessel oxygenation level and the evolution of the oxygenation level. The initial image analysis can be followed by machine learning to distinguish between a normal retina and a retina affected by a disease (the ophthalmologist's diagnosis can be taken as ground truth).

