7.2. Population for analysis

Safety Population

The population for the assessment of safety will include all enrolled subjects who provide at least the investigation performance phase (visit 1 - part2).

PP population

The Per Protocol (PP) population will include all subjects without significant protocol violations. Subjects identified as protocol violators will be documented and agreed upon before declaration of clean-file.

Population size

An estimated 120 people will be recruited for the study:

- Approximately 100 male or female subjects, 18 years or older, with an ophthalmological disease, disorder, illness or problem will be recruited in this investigation.
- Approximately 20 healthy male or female subjects, 18 years or older, will be recruited in this investigation.

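### The healthy-versus-disease questions rest on 20 volunteers with no link to patient age and no diabetes, and no planned analysis separates disease from either

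*Combined protocol and SAP*

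**What the plan says.** Section 6.1 describes a single-centre, open, controlled investigation, and 7.1 (Presentation of the data) repeats that label. Section 6.1 then explains that no treatment effect is to be shown and concludes: "Thus, no control group is defined".

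Three places nevertheless set normal against diseased retina:

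- The Synopsis primary endpoint asks: "Can the hyperspectral camera detect differences in oxygenation levels between arteries and veins in healthy retina and retina with disease".
- The secondary objective in 5.2 asks whether changes seen only by the camera differ from normal retinal changes.
- Section 6.4 allows a later step of "machine learning to distinguish between a normal retina and a retina affected by a disease".

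On group sizes, 7.2 says "Approximately 20 healthy male or female subjects, 18 years or older, will be recruited in this investigation" and "Approximately 100 male or female subjects, 18 years or older, with an ophthalmological disease, disorder, illness or problem will be recruited in this investigation". On recruitment, 6.4 says "Recruitment of healthy subjects is done through local advertising", while patients come from the clinic. In 6.3 the only age rule for either group is over 18 years. The healthy exclusion reads "Presence of eye disease, eye trauma, diabetes or pregnancy"; the patient list has no counterpart. Section 3.1 says that "more and more people are also suffering from age-related diseases such as glaucoma and yellow spot changes".

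Age, sex, other diseases and treatment are recorded at visit 1 (6.4). Section 7.3 summarises baseline variables, and 7.1 limits the analysis to descriptive statistics without hypothesis testing.

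**The concern.** The absence of a treatment comparison is a sound reason for having no treatment control. It is not a reason for leaving the normal reference undefined when the plan asks how diseased retina differs from normal. The volunteers fill that role by default, and nothing makes them resemble the patients in age. Because 3.1 itself calls two of the target diseases age-related, an older patient group is a reasonable expectation.

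Diabetes is absent from the healthy side by rule and permitted on the patient side. For a comparison with diabetic retinopathy that is part of the contrast. For a comparison with glaucoma or macular disease it is an extra difference between the groups.

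At stake is the reading of any between-group oxygenation difference and of any classifier. A classifier trained on these two groups could score well by separating younger from older eyes. Being descriptive does not protect the study: a summary difference is confounded in the same way as a test.

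**Working it through.** **Plan's own figure.** 100 + 20 = 120, as stated. The plan gives no effect size, SD or age distribution, so no sample-size formula can be reproduced and no bias can be computed from the documents. What follows is illustration under assumptions.

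**Precision of the contrast.** In units of the between-subject SD, SE = sqrt(1/20 + 1/100) = 0.245. The 95% half-width is 1.96 x 0.245 = 0.48 SD.

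**Illustration 1, saturation points.** Assumed: age gap 20 to 30 years, shift in estimated saturation 0.5 to 2 points per decade, SD 8 points.

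- Bias: 0.5 x 2 = 1 point to 2 x 3 = 6 points.
- SE: 8 x 0.245 = 1.96 points.
- Ratio: 1/1.96 = 0.5 to 6/1.96 = 3.1 standard errors.

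**Illustration 2, SD units.** Assumed: within-group age SD 12 to 15 years, within-group age-oxygenation correlation r of 0.1 to 0.4, no disease effect. Bias = r x (gap / age SD). The chance that an unadjusted 95% interval excludes zero is Φ(bias/SE − 1.96) + Φ(−bias/SE − 1.96), which is 0.05 without bias.

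| Age gap, age SD (years) | Bias, r = 0.1 to 0.4 (SD) | Bias (SE) | Chance interval excludes 0 |
|---|---|---|---|
| 0, either | 0 | 0 | 0.05 |
| 10, 15 | 0.07 to 0.27 | 0.3 to 1.1 | 0.06 to 0.19 |
| 20, 12 | 0.17 to 0.67 | 0.7 to 2.7 | 0.10 to 0.78 |
| 30, 12 | 0.25 to 1.00 | 1.0 to 4.1 | 0.18 to 0.98 |

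The two illustrations agree. With age SD 12 and outcome SD 8, slopes of 0.5 and 2 points per decade correspond to r = 0.05 x 12/8 = 0.075 and 0.20 x 12/8 = 0.30. The second runs higher only because it lets r reach 0.4.

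**What adjustment would cost.** Age-adjusted SE = 0.245 x sqrt[(1 + (1/6)(5/6)(gap/age SD)²) x (1 − r²)]. Over gaps of 10 to 30 years the 95% half-width is 0.45 to 0.65 SD, against 0.48 unadjusted. Comparing the 20 volunteers with only 20 age-matched patients gives 1.96 x sqrt(2/20) = 0.62 SD. Both are usable for a pilot, but linear adjustment is trustworthy only where the age ranges overlap.

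**Which aims are exposed.**

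| Aim | Needs comparable groups? |
|---|---|
| 5.2 primary: structures, repeatability, healthy artery above 95% and vein below 70% | No |
| Artery-vein difference within an eye (6.4) | Largely no: a shift common to both vessels cancels |
| Healthy-versus-disease reading of the Synopsis primary endpoint | Yes |
| Secondary question on normal retinal changes | Yes |
| Classifier (6.4, optional) | Yes |

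The illustrations model a shift in saturation level. They do not measure bias in the artery-vein difference, which would be distorted only if that difference itself changes with age or diabetes.

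**The case against.** The strongest reply is that this is a pilot aimed at feasibility (3.4, 6.1), sized for exploratory trends (the sample-size paragraph of section 7), with no planned test and no planned analysis that attributes a difference to disease. The camera is also to be compared with other techniques and with expert diagnosis, so healthy subjects are not the only comparator. This limits the consequences. It does not remove the point: those comparisons do not supply normal retinas, and the plan still poses questions that need them.

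A reader might go further and infer that a healthy-versus-disease difference can never be assigned to disease. The documents do not support that. Age and other diseases are recorded for every subject, so restriction or stratification is possible wherever ages overlap. Nothing shows that they fail to: both groups are simply over 18, and the patients also include diabetes and retinal detachment.

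Nor is excluding retinal disease from the healthy group a flaw, since it defines the contrast. Excluding any eye disease could also leave the volunteers with clearer ocular media than the patients, but that is inference: the documents do not discuss media opacity, and 6.4 names a corneal microscope examination without saying that lens or media findings are recorded.

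**Conclusion.** The point holds in limited form. As written, a crude healthy-versus-disease difference or a classifier result would mix disease with age and diabetes, because neither recruitment nor analysis deals with them. It does not touch the 5.2 primary outcomes, and it is an improvement the plan should make rather than a defect that invalidates the study.

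The size is unknown. About 0.5 to 3 standard errors follows from an assumed 20 to 30 year gap, 0.5 to 2 points per decade and an SD of 8 points. With no age gap the age bias is zero; with a 10-year gap it can be as small as 0.3 standard errors. That the gap exists is an expectation drawn from 3.1, not a documented fact.

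**What to change.** 1. **6.1:** reconcile the controlled label with the statement on control groups, and name the 20 healthy subjects as the reference group for the healthy-versus-disease questions.
2. **6.3 and 6.4:** fill the 20 healthy places by age band in line with the clinic's retinal patients, through targeted advertising. Fix the bands in advance from the clinic's usual age profile, because 6.5 ends healthy recruitment in November 2022, a month before patient recruitment ends. Totals stay at 20 and 100.
3. **7.4:** show the healthy-versus-disease contrast, and any classifier result, within the overlapping age range or by age stratum, with confidence intervals. Repeat it for patients without diabetes. The age and other-disease data recorded at visit 1 suffice.
4. **7.4:** state that unadjusted group differences will not be attributed to disease.

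A display that leaves out eyes with media opacity should not be promised unless the CRF captures that finding.

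**Cost:** protocol wording, advertising text and a few extra tables. Older volunteers without eye disease are harder to find, so healthy recruitment may run past the October-November 2022 window in 6.5 and delay the healthy-data analysis due to start in December. The Synopsis allows subjects until Q2 2023, so the two timelines need to be squared. Age banding also changes which healthy people are held against the 95% and 70% limits in 5.2, and the sponsor should accept that knowingly. If recruitment is already complete, items 1, 3 and 4 can still be adopted.
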